Heart failure	Outcome: changes in use in patients with VTE risk factors	Defined as ≥1 ICD-10 diagnosis code for heart failure while receiving tofacitinib therapy.
Use of combined hormonal contraceptives or hormonal replacement therapy	Outcome: changes in use in patients with VTE risk factors	Defined as ≥1 prescription dispensing of a combined hormonal contraceptives and/or hormonal replacement therapy (as identified by ATC codes) while receiving tofacitinib therapy.
Inherited coagulation disorder	Outcome: changes in use in patients with VTE risk factors	Defined as ≥1 ICD-10 diagnosis code for inherited coagulation disorder while receiving tofacitinib therapy.
Malignancy (non- metastatic and metastatic, excluding NMSC)	Outcome: changes in use in patients with VTE risk factors	Defined as ≥1 ICD-10 diagnosis code for malignancy (excluding NMSC) while receiving tofacitinib therapy.
Age ≥ 65 years	Outcome: changes in use in patients with VTE risk factors	Defined as age ≥65 years while receiving to facitinib.
Diabetes	Outcome: changes in use in patients with VTE risk factors	Defined as ≥1 ICD-10 diagnosis code for diabetes or ≥3 (or at least 2 in case of large pack sizes) prescription dispensing of oral antidiabetic agents and/or insulin (identified by ATC codes) while receiving tofacitinib therapy.
Hypertension	Outcome: changes in use in patients with VTE risk factors	Defined as ≥1 ICD-10 diagnosis code for hypertension or ≥3 (or at least 2 in case of large pack sizes) prescription dispensing of antihypertensive agents (identified by ATC codes) while receiving tofacitinib therapy.
Discontinuation of tofacitinib after developing ≥1 VTE risk factors while taking tofacitinib	Outcome: changes in use in patients with VTE risk factors	Defined as ≥1 VTE risk factor(s) while receiving tofacitinib therapy (as listed and defined above) plus 0 prescription dispensing for tofacitinib within a specific time window after the code for the first VTE risk factor.
g		Note: The time window for when to look for a tofacitinib prescription dispensing will be specific to the VTE risk factor(s) acquired while receiving tofacitinib therapy and will be operationalised during SAP development.
		Duration of tofacitinib therapy defined in Section 9.3.2.

Table 3. Operational definitions of study variables in Système National des Données de Santé

Variable Role Operational definition	
Discontinuation of Outcome: changes The same definition as above but of	only limited to VTE risk

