Variable	Role	Operational definition
Continuation of	Outcome: changes	Defined as patients aged <65 years when initiating
tofacitinib for patients	in use in patients	tofacitinib, who have ≥1 prescription dispensing of
who turn 65 years old	aged 65 years and	tofacitinib within a specific time window after turning 65
while receiving	older	years and ≥1 prescription dispensing for an alternative
tofacitinib with prior		therapy (i.e., biologic) prior to index tofacitinib prescription
use of alternative		dispensing.
therapies		
	endations for limitation	ons of use in patients with CV risk factors (will be stratified
		, and CV and malignancy report period 1, 2, 3)
Assessment of CV risk for	actors prior to initiation	n of tofacitinib
History of	Outcome: changes	Defined as ≥1 ICD-10 diagnosis code for hyperlipidaemia or
hyperlipidaemia	in use in patients	≥1 prescription dispensing (as identified by ATC code[s]) for
	with CV risk	a statin or other antihyperlipidaemic in the 12 months prior
	factors	to the index tofacitinib dispensing.
		Complete list in ANNEX 9. LIST OF ATC CODES FOR
		ANTIHYPERLIPIDAEMICS.
Age ≥65 years	Outcome: changes	Defined as age at tofacitinib initiation ≥65 years
	in use in patients	
	with CV risk	
	factors	
History of coronary	Outcome: changes	Defined as ≥1 ICD-10 diagnosis code for MI or stroke or ≥1
artery disease (defined	in use in patients	procedure code for CABG or PCI in the 12 months prior to
as MI, stroke,	with CV risk	the index tofacitinib dispensing.
coronary artery bypass	factors	
graft [CABG] or		
percutaneous coronary		
intervention [PCI])		
History of stable	Outcome: changes	Defined as ≥1 ICD-10 code for stable angina pectoris in the
angina pectoris	in use in patients	12 months prior to the index tofacitinib dispensing.
	with CV risk	
	factors	
Current or past	Outcome: changes	Defined as ≥1 ICD-10 diagnosis code for tobacco use
smoker ¹	in use in patients	disorder or ≥1 procedure code for counselling visits for
	with CV risk	smoking or ≥1 prescription dispensing (as identified by ATC
	factors	code[s]) for a nicotine replacement product in the 12 months
		prior to the index tofacitinib dispensing.
History of diabetes	Outcome: changes	Defined as ≥1 ICD-10 diagnosis code for diabetes or at least
	in use in patients	3 reimbursements (or at least 2 in case of large pack sizes) of
	with CV risk	oral antidiabetic agents and/or insulin in the 12 months prior
	factors	to the index tofacitinib dispensing.

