Hyperlipidaemia	Outcome: changes in use in patients with CV risk factors	Defined as ≥1 ICD-10 diagnosis code for hyperlipidaemia or ≥1 prescription dispensing (as identified by ATC code[s]) for a statin or other antihyperlipidaemic while receiving tofacitinib. Complete list in ANNEX 9. LIST OF ATC CODES FOR ANTIHYPERLIPIDAEMICS.
Age ≥65 years	Outcome: changes in use in patients with CV risk factors	Defined as age ≥65 years while receiving tofacitinib.
Current smoker	Outcome: changes in use in patients with CV risk factors	Defined as ≥1 ICD-10 diagnosis code for tobacco use disorder or ≥1 procedure code for counselling visits for smoking or ≥1 prescription dispensing (as identified by ATC code[s]) for a nicotine replacement product while receiving tofacitinib.
Coronary artery disease (defined as MI, stroke, CABG or PCI)	Outcome: changes in use in patients with CV risk factors	Defined as ≥1 ICD-10 diagnosis code for MI or stroke or ≥1 procedure code for CABG or PCI while receiving tofacitinib therapy.

Table 3. Operational definitions of study variables in Système National des Données de Santé

Variable	Role	Operational definition
Stable angina pectoris	Outcome: changes	Defined as ≥1 ICD-10 diagnosis code for stable angina
8 ₁	in use in patients	pectoris while receiving tofacitinib therapy.
	with CV risk	
	factors	
Diabetes	Outcome: changes	Defined as ≥1 ICD-10 diagnosis code for diabetes while
	in use in patients	receiving tofacitinib therapy.
	with CV risk	
	factors	
Hypertension	Outcome: changes	Defined as ≥1 ICD-10 diagnosis code for hypertension or ≥1
	in use in patients	prescription dispensing (as identified by ATC code[s]) for an
	with CV risk	antihypertensive while receiving tofacitinib.
	factors	Complete list in ANNEX 8. LIST OF ATC CODES FOR
		ANTIHYPERTENSIVES.
Chronic kidney	Outcome: changes	Defined as ≥1 ICD-10 diagnosis code for chronic kidney
disease	in use in patients	disease while receiving tofacitinib.
	with CV risk	
Discontinuation of	factors	Defined as >1 CV misk featon(a) while massiving tofesitinih
tofacitinib after	Outcome: changes	Defined as ≥1 CV risk factor(s) while receiving to facitinib therapy (as listed and defined above) plus 0 prescription
	in use in patients with CV risk	dispensing for tofacitinib within a specific time window after
developing ≥1 CV risk factors while taking	factors	the code for the first CV risk factor.
tofacitinib	Tactors	the code for the first C v fisk factor.

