Preliminary data from the first interim report of the ongoing DUS study (A3921321) suggests that 30 to 80% of tofacitinib initiators had one or more risk factors of interest at baseline (e.g., during reporting period 1). Sample size was calculated across a range of possible baseline proportions and meaningful differences between any two reporting periods. Given the challenges in defining minimum meaningful differences and the lack of scientific guidance or validated thresholds, Chen et al.'s rule of thumb for classifying the magnitude of effect size based on odds ratios (OR) (e.g., small effect) is used to inform the minimum meaningful difference. Minimum sample size is determined based on the smallest sample size needed to detect a minimum meaningful difference per scenario of baseline proportion. It is thus estimated that 160 to 354 patients per reporting period (480 to 1,062 total patients) per indication group (e.g., RA/PsA and UC) are needed to detect a minimum meaningful difference with 80% statistical power ($\beta = 0.20$) and a two-sided 5% significance level ($\alpha = 0.05$) (Table 1**Error! Reference source not found.**). Sample size needed varies based on the baseline proportion and point percent difference between reporting periods. The required sample size is irrespective of the length of the reporting period.

Table 5.	Sample size for comparing changes in the proportion of patients with risk
	factors of interest across reporting periods

Percentage of patients with at least one risk factors at baseline	Point percent difference between any two reporting periods	Effect size classification for the difference based on OR ^a	Number of patients needed per reporting period ^b	Total number of patients needed for the entire study period per indication group b, c
80%	10%	Small	291	873
70%	10%	Small	354	1,062
70%	15%	Small	160	480
60%	10%	Small	385	1,155
60%	15%	Small	171	513
50%	10%	Small	385	1,155
50%	15%	Small	167	501
40%	10%	Small	354	1,062
30%	10%	Small	291	873

Odds ratio = VTE reporting period X odds of outcome / VTE reporting period Y odds of outcome; Classified effect sizes as weak ($1 \le OR < 1.5$), small ($1.5 \le OR < 2$), medium ($2 \le OR < 3$) and large (≥ 3).

Comparative analyses for the changes in composite risk factor scores

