9.7.2.4.3. Patients with cardiovascular risk factors

To describe changes in the utilisation of tofacitinib, this analysis will be stratified by the CV and malignancy reporting periods 1, 2 and 3. The proportion of patients with one or more CV risk factors, identified prior to tofacitinib initiation, will be described and tabulated overall and for each individual CV risk factor.

Logistic regression analyses will be used to calculate odds ratios along with their corresponding 95% confidence intervals and p values to formally compare the proportion of patients with CV risk factors across CV and malignancy reporting periods 1, 2 and 3.

To enhance statistical power in detecting changes, a composite score for the CV risk factors will also be generated by summing the individual CV risk factors. Linear regression analyses will be employed to compare the CV composite score across the CV and malignancy reporting periods. In addition to the summed composite score, the same analysis using a composite score weighting the risk factors may be performed in an exploratory fashion (weights will be developed and described in the SAP). Regression coefficients with their 95% confidence intervals and p values will be generated.

Proportions will be stratified by sex, age (≥65 years versus < 65 years) and prior use of alternative therapy (e.g., biologic), pending sufficient sample size.

The proportion of patients who discontinue or continue to facitinib after developing one or more CV risk factors while taking to facitinib will be described separately. The proportion will be further stratified by sex, age (≥65 years versus < 65 years) and prior use of alternative therapy (e.g., biologic), pending sufficient sample size.

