9.7.2.4.4. Patients with malignancy risk factors

To describe changes in the utilisation of tofacitinib, this analysis will be stratified by the CV and malignancy reporting periods 1, 2 and 3. The proportion of patients with one or more malignancy risk factors, identified prior to tofacitinib initiation, will be described and tabulated overall and for each individual malignancy risk factor.

Logistic regression analyses will be used to calculate odds ratios along with their corresponding 95% confidence intervals and p values to formally compare the proportion of patients with malignancy risk factors across CV and malignancy reporting period 1, 2 and 3.

To enhance statistical power in detecting changes, a composite score for the malignancy risk factors will also be generated by summing the individual malignancy risk factors. Linear regression analyses will be employed to compare the malignancy composite score across the CV and malignancy reporting periods. In addition to the summed composite score, the same analysis using a composite score weighting the risk factors may be performed in an exploratory fashion (weights will be developed and described in the SAP). Regression coefficients with their 95% confidence intervals and p values will be generated.

Proportions may be stratified by age (≥65 years versus < 65 years) and prior use of alternative therapy (e.g., biologic), pending sufficient sample size.

The proportion of patients who discontinue or continue to facitinib after developing one or more malignancy risk factors while taking to facitinib will be described separately. Proportions will be stratified by age (≥65 years versus < 65 years) and prior use of alternative therapy (e.g., biologic), pending sufficient sample size.

9.7.2.5. Describe prescribing patterns over time: Describe changes in the utilisation of tofacitinib following the updated recommendations and limitations for use implemented after the JAKi 2022/2023 Article 20 referral

9.7.2.5.1. UC maintenance treatment dosage for patients with CV and malignancy risks, in addition to VTE risk factors

To describe changes in the utilisation of tofacitinib, this analysis will be stratified by the JAKi reporting periods 1, 2 and 3. The proportion of UC patients with CV or malignancy risk factors who have an ADD of > 10 mg in Weeks 17-24, Weeks 25-32, Weeks 33-40 and/or Weeks 41-48 of follow-up will be described and tabulated over each of the JAKi reporting periods.

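### Outcomes after developing a risk factor on treatment do not require the factor to be new, and in age-stratified CV and malignancy tables the proportion with at least one factor is fixed at 100% from age 65

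*Protocol*

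**What the plan says.** Section 9.3.1, Table 3, lists VTE, CV and malignancy risk factors twice: once before initiation and once while on therapy. The on-treatment lists feed paired outcomes, discontinuation and continuation after developing at least one factor. For VTE the discontinuation outcome is "Defined as ≥1 VTE risk factor(s) while receiving tofacitinib therapy (as listed and defined above) plus 0 prescription dispensing for tofacitinib" within a time window that starts at the code for the first factor. The CV and malignancy versions are built the same way. The outcome titles say *developing* and the notes say *acquired*. Those notes leave only the length of the time window to the SAP.

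Age is in all three on-treatment lists: "Defined as age ≥65 years while receiving tofacitinib" for CV, and the same rule for VTE and malignancy. At initiation, age is also a CV and a malignancy factor: "Defined as age at tofacitinib initiation ≥65 years".

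Section 9.7.2.4.3 says that the proportions who stop or continue "after developing one or more CV risk factors while taking to facitinib will be described separately". For the CV analysis it adds: "Proportions will be stratified by sex, age (≥65 years versus < 65 years) and prior use of alternative therapy". Section 9.7.2.4.4 says of malignancy at initiation: "Proportions may be stratified by age (≥65 years versus < 65 years) and prior use of alternative therapy". Both are subject to sufficient sample size.

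**The concern.** There are two separate problems.

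1. The label promises a new factor, but the operational text counts any factor recorded on therapy. A patient who already had the factor and simply stays on tofacitinib is then counted as continuing despite a newly acquired risk. A reader of the report would take this as evidence about how prescribers respond to new risk.

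2. The CV and malignancy proportions are split by a variable that is itself one of the factors being counted. In the older stratum the headline proportion is then fixed by definition and says nothing about change after the revised risk minimisation materials.

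**Working it through.** The protocol states no figure for either problem, so there is none to reproduce. The check sets the definitions side by side.

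**Part 1: what triggers each on-treatment factor (Table 3)**

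| List and factor | Trigger on therapy | Can a pre-existing factor meet it? |
|---|---|---|
| CV hyperlipidaemia | diagnosis code or 1 lipid-lowering dispensing | yes, at the next fill |
| CV hypertension | diagnosis code or 1 antihypertensive dispensing | yes, at the next fill |
| CV diabetes | diagnosis code only | yes if the code repeats; a refill does not count |
| VTE diabetes, hypertension | diagnosis code, or at least 3 dispensings (2 for large packs) | yes, after enough continuing fills or a repeated code |
| VTE hormonal therapy | 1 dispensing | yes, at the next fill |
| Smoking (CV, malignancy) | code, counselling visit or 1 nicotine-replacement dispensing | yes |
| Heart failure, coagulation disorder, chronic kidney disease, malignancy | diagnosis code | yes, if the code repeats |
| Major surgery, CABG/PCI | procedure code | no, needs a new procedure |
| VTE, MI, stroke | diagnosis code | normally a new event; a repeated code would also count |
| Age (all three lists) | 65 or older at any time on therapy | yes, on day 1 if 65 or older at index |

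No row carries an absent-at-baseline condition. The separate Table 3 variables for patients who turn 65 on treatment do require age under 65 at initiation, so the protocol applies the restriction there and omits it here.

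The time window makes this worse. It starts at the code for the first factor, and age has no code, so its start is undefined. If an old factor is re-recorded early, a genuinely new event later in follow-up is not the first factor, and the response to it is not what is measured.

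*Illustration, on assumptions only.* Let b be the share with a factor at baseline, r the share of those re-recorded on therapy, and i the new-onset share among the rest. This ignores a second, different factor arising in someone who already has one.

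- Share flagged as having developed a factor = b·r + (1 − b)·i
- Truly new share of those flagged = (1 − b)·i / [b·r + (1 − b)·i]

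Section 9.5, citing the other drug utilisation study, "suggests that 30 to 80% of tofacitinib initiators had one or more risk factors of interest at baseline". I therefore take b from 0.30 to 0.80. I assume r from 0.8 to 1.0 and i from 0.02 to 0.10; the protocol gives neither.

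- b = 0.30: lowest 0.014/0.314 = 4.5%; highest 0.07/0.31 = 22.6%
- b = 0.50: lowest 0.01/0.51 = 2.0%; highest 0.05/0.45 = 11.1%
- b = 0.80: lowest 0.004/0.804 = 0.5%; highest 0.02/0.66 = 3.0%

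The result depends heavily on r. With b = 0.30, i = 0.10 and r halved to 0.4, the truly new share is 0.07/(0.12 + 0.07) = 36.8%. The direction is clear; the size is not.

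**Part 2: the older stratum**

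Let q be the prevalence of at least one factor other than age among patients aged 65 or older. Because age is in the list:

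- P(at least one factor | 65 or older) = 1 − (1 − 1)(1 − q) = 1

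So q = 0.30, 0.60 or 0.90 all give 100%, in reporting periods 1, 2 and 3 alike. With age left out of the flag, the same cells read 30%, 60% and 90%.

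**The case against.** Much can be said for the plan. The words *developing* and *acquired* show that new onset is intended. Section 9.3.1 calls its algorithms preliminary and allows refinement in the SAP. Patients who turn 65 on therapy have their own correctly restricted variables. The stop and continue proportions are only to be described. All of this stands and limits the severity. It does not remove the conflict: the specific notes defer only the time window, and whether a factor must be new is a condition of the outcome, not a code list.

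Four stronger readings are tempting, and the protocol does not support them.

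- *Any chronic drug triggers a factor at the first refill.* This is not so for CV diabetes, which needs a diagnosis code, or for VTE diabetes and hypertension, which need at least 3 dispensings (2 for large packs).
- *The 30 to 80% range can be applied to the projected 8,000 RA or PsA patients to count those misclassified* (2,400 to 6,400). That range comes from a study in Sweden, Hungary, Germany and the Netherlands and is not specific to RA or PsA. The count also needs a re-recording rate that the protocol does not give.
- *The older stratum carries no information and its odds ratio cannot be estimated.* Only the at-least-one-factor proportion and the age row are fixed. The other individual factors vary, as does having a factor without a prior biologic. The summed score varies too, because age adds the same 1 to everyone in the stratum. The protocol specifies no odds ratio within age strata.
- *VTE is affected by the age split.* Section 9.7.2.4.1 plans no age stratification; only the first problem reaches VTE.

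**Conclusion.** Both problems follow from the wording of the protocol and need no data to establish.

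1. As written, the outcomes after developing a VTE, CV or malignancy factor can count pre-existing factors, including age 65 or older at index, as new. They would blend ordinary persistence with the response to new risk. The proportion of each cannot be derived from the protocol; the percentages worked above rest on assumed re-recording and new-onset rates and only show the direction.

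2. In patients aged 65 or older, the proportion with at least one CV factor, and with at least one malignancy factor if that table is produced, is exactly 100% in every reporting period. This assumes only that the flag uses the list as printed.

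A reader might infer that the main results are compromised. They are not: Section 9.5 makes the primary comparison reporting period 3 against period 1 in initiators with risk factors, which uses the baseline definitions without the age split. Should-fix. The SAP is not at hand and may already resolve part of this.

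**What to change.** 1. For the stop and continue outcomes, count an on-treatment factor only if there was no qualifying code, procedure or dispensing for that same factor in the 12-month baseline. For age, require under 65 at index and a 65th birthday on therapy. Date the factor at its first new record, or at the 65th birthday, and start the time window there.

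2. In every age-stratified table, compute the flags for at least one CV factor and at least one malignancy factor without the age item, and say so in a footnote. The summed score can stay as it is, since age is constant within each stratum at initiation.

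The cost is wording in Table 3 or the SAP; the baseline data are already to be collected. The denominators of the on-treatment outcomes become smaller. A repeat event in a patient who had the same event at baseline would no longer count, which should be stated. The sponsor should also decide whether the first change is a major modification of a primary endpoint definition, for which Section 9.7 foresees a protocol amendment.

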9.9.1.2. Information bias

Diagnoses

There is the potential for misreporting of information in the existing health system from where the data are retrieved (medical records and national registry). However, for the variables that are to be collected for the present study, experience from previous research shows that the reporting to French SNDS database and linked dataset is reasonable. Furthermore, chronic diagnoses as per the LTD database are approved by physicians of the health care insurance system, and choice of hospital diagnoses is guided by comprehensive coding instructions to enhance the homogeneity of data input. That the choice of diagnosis code is independent from the study team also facilitates the avoidance of information bias.

The identification of comorbidities in the SNDS does not rely on data from a single source, instead relying on validated algorithms using diagnoses, treatment and procedure data thereby decreasing risk of misclassification of these conditions. ^{24, 29} Specific algorithms are implemented to capture diagnosis performed outside of hospital as limited information on diagnosis (ICD-10 codes as per the registration in the LTD database only) is available in outpatient settings. ³⁰ As such, the algorithms will utilise data on procedures, diagnosis codes as per the LTD database (where available) and reimbursed prescriptions, as relevant. Published, validated algorithms will be used where available. ^{6, 7}

Laboratory data

Although laboratory results are not reported in the datasets to be employed, adherence to the laboratory screening and monitoring can only be assessed at the level of whether a laboratory was done rather than the actual value. This limits the study's ability to evaluate whether a prescriber should properly continue or discontinue to facitinib treatment according to laboratory results. As part of the development of the SAP, procedure codes for the screening and laboratory tests of interest will be identified and confirmed with the database owner/local clinicians. If procedure codes are not available for a given test, this will be noted in the SAP.

Other comorbidities (e.g., lifestyle risk factors)

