ANNEX 11. LIST OF CODES FOR COMORBIDITIES

Comorbidity	Definition	Codes (ICD-10 codes, ATC codes, CCAM procedure codes)
Hepatic impairment	Defined as ≥1 ICD-10 diagnosis code for hepatic impairment.	K71 and K72
Renal impairment	Defined as ≥1 ICD-10 diagnosis code for renal impairment or a combination of EBM service	Stage III, IV or V (end stage) Chronic kidney disease
	codes, ICD-10 diagnosis codes and/or ICD-10 procedure codes.	ICD-10 diagnosis: Specific diagnoses of CKD Stage 3: N183 Stage 4: N184 Stage 5: N185 Other chronic renal disease: N188 and N189
		Diagnoses linked to CKD stage 5 Hypertensive cardionephropathy, with renal failure: I131 and I132 Extra-corporeal dialysis: Z491 Preparatory care for dialysis: Z490 Failure and rejection of a kidney transplant: T861 Dependence to kidney dialysis: Z992+1
		CCAM codes for medical procedures due to kidney failure (stage 5): JVJF002, JVJF004, JVJF003, JVJF005, JVJF006, JVJF007, JVJF008, JVRP004, JVRP007, JVRP008 and YYYY007 [TBC IN LAST VERSION]
Diabetes	Defined as ≥1 ICD-10 diagnosis code for diabetes or at least 3 reimbursements (or at least 2 in case of large pack sizes) of oral antidiabetes agents and/or insulin.	ICD-10 diagnosis: E10-E14 ATC code medications: A10*
Herpes zoster	Defined as ≥1 ICD-10 diagnosis code for herpes zoster.	B02*
Human immunodeficiency virus	Defined as ≥1 ICD-10 diagnosis code for human immunodeficiency virus.	B20-B24 and Z21
Tuberculosis, including both active and latent TB	Defined as ≥1 ICD-10 diagnosis code for tuberculosis.	
Viral hepatitis B or C	Defined as ≥1 ICD-10 diagnosis code for viral hepatitis B or C.	B180, B181 and B182

Comorbidity	Definition	Codes (ICD-10 codes, ATC codes, CCAM procedure codes)
Diverticulitis	Defined as ≥1 ICD-10 diagnosis code for diverticulitis.	Q396, Q696, K225, K382, N323, Q430, K314, N361 and C173
Malignancy (non-metastatic and metastatic, excluding non-melanoma skin cancer)	Defined as ≥1 ICD-10 diagnosis code for a malignancy (excluding non-melanoma skin cancer).	See table below
Non-melanoma skin cancer	Defined as ≥1 ICD-10 diagnosis code for non-melanoma skin cancer.	C44 other malignant tumour of the skin
Gastrointestinal perforation	Defined as ≥1 ICD-10 diagnosis code for gastrointestinal perforation.	K285

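### Table 3 defines diabetes as an on-treatment CV risk factor by diagnosis code alone, while the protocol's five other diabetes definitions also accept repeat antidiabetic dispensings

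*Protocol*

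**What the plan says.** The protocol defines diabetes six times.

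- **CV risk factor on treatment (Table 3):** "Defined as ≥1 ICD-10 diagnosis code for diabetes while" receiving tofacitinib. Nothing else qualifies.
- **CV risk factor at baseline (Table 3):** "Defined as ≥1 ICD-10 diagnosis code for diabetes or at least" "3 reimbursements (or at least 2 in case of large pack sizes) of" oral antidiabetics and/or insulin.
- **VTE risk factor on treatment (Table 3):** "Defined as ≥1 ICD-10 diagnosis code for diabetes or ≥3 (or at least 2 in case of large pack sizes) prescription dispensing" of the same drugs. The VTE baseline row and the comorbidity row use the same rule.
- **Annex 11:** a diagnosis code (E10-E14) "or at least 3 reimbursements (or at least 2 in case of large pack sizes) of oral antidiabetes agents and/or insulin", with the drugs identified as A10*.

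The CV discontinuation outcome takes its risk factors from the on-treatment list ("as listed and defined above) plus 0 prescription" dispensing of tofacitinib in a set window after the first factor). The CV continuation outcome uses the same list.

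On the data source, Section 9.9.1.2 notes that "limited information on diagnosis (ICD-10 codes as per the registration in the LTD database only) is available in outpatient settings". It adds that the algorithms will draw on procedures, LTD codes and reimbursed prescriptions, as relevant.

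**The concern.** One condition has two incompatible rules, and the stricter one sits where the data source is weakest. New diabetes managed outside hospital may have no ICD-10 code until the patient is registered for LTD, and the dispensing route exists to catch such patients. Without it, the same records give diabetes as a CV factor before index but not after it, and diabetes for the VTE on-treatment outcomes but not for the CV ones. A programmer working from Annex 11 and one working from this Table 3 row would build different variables. At stake are which patients enter the CV discontinuation and continuation outcomes and when their window starts. For ulcerative colitis (UC), the high-maintenance-dose outcome in the JAKi referral analysis is also exposed.

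**Working it through.** No arithmetic in the plan bears on this point, so the check sets the definitions side by side and traces where the row is used.

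**1. Definitions compared**

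| Place | ICD-10 code | ≥3 dispensings (≥2 large pack) |
|---|---|---|
| Table 3, comorbidity | yes | yes |
| Table 3, VTE baseline | yes | yes |
| Table 3, VTE on treatment | yes | yes |
| Table 3, CV baseline | yes | yes |
| Annex 11 | yes | yes |
| Table 3, CV on treatment | yes | **no** |

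Five of six accept dispensings. Relying on codes alone is not a general rule for the on-treatment CV list either: its hyperlipidaemia and hypertension rows each accept a single dispensing.

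**2. Who is misclassified.** The patients concerned have qualifying antidiabetic dispensings while on tofacitinib and no hospital or LTD diabetes code in that time. Anyone with a code is counted under either rule.

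**3. Where the row is used**

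- *CV discontinuation and continuation (Table 3; Section 9.7.2.4.3).* Both use the on-treatment CV list. They are described by CV and malignancy reporting period and, sample size permitting, by sex, age and prior biologic.
- *JAKi UC maintenance-dose outcome (Table 3; Section 9.7.2.5.1).* It needs at least one CV or malignancy factor from baseline to Week 16. On a natural reading, the stretch from index to Week 16 uses the on-treatment rows. It is compared across JAKi reporting periods by regression.
- *UC posology outcome (Table 3, ADD >10 mg with VTE, CV or malignancy factors up to Week 16).* It refers to CV factors over the same window, but it also accepts VTE factors. The VTE on-treatment row should bring in the same patient, so membership should not change here.
- *Not affected:* the logistic and linear regressions of CV risk factors and the CV score in Section 9.7.2.4.3, which use factors identified before initiation, and the VTE discontinuation and continuation outcomes.

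**4. When it changes a result.** The on-treatment CV list has eight factors: hyperlipidaemia, age ≥65, smoking, coronary artery disease, stable angina, diabetes, hypertension and chronic kidney disease. A patient missed on diabetes leaves the group only if none of the other seven is recorded. If another is recorded later than the diabetes, the patient stays in but the discontinuation window starts late.

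Let w be the share of the full group that is missed, p₁ the proportion discontinuing among those counted and p₂ among those missed. The full-group proportion is (1 − w)p₁ + w·p₂, so the reported value differs from it by p₁ − [(1 − w)p₁ + w·p₂] = w(p₁ − p₂). The documents give none of w, p₁ or p₂.

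**The case against.** Section 9.3.1 calls the algorithms preliminary and lets the SAP refine them, Annex 11 already has the A10* rule, and Section 9.9.1.2 commits to prescriptions where relevant. This lowers the practical risk. It does not remove the contradiction: the row is not left open, it states a rule that conflicts with the others.

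The dispensing rule also has faults of its own, and this objection stands. Discontinuation is timed from the code for the first factor, and a rule of three dispensings has no stated event date. The dispensings must accrue while the patient receives tofacitinib, so someone who stops soon after a first antidiabetic dispensing may never qualify, which would tilt the result towards continuation. Nor does the row require diabetes to be absent at baseline. The VTE on-treatment row shares all of this, so copying its wording is not enough.

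Three stronger readings are tempting, and the documents support none of them.

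- *Only the CV discontinuation outcome is hit.* The continuation outcome uses the same list, and the JAKi UC outcome is exposed up to Week 16.
- *A large share of events is lost.* If 30-60% of new diabetes were visible only through dispensings, the CV row would find 40-70% of diabetes events. That is merely the complement of an assumption nothing in the protocol anchors, and it describes diabetes events rather than the outcome of at least one factor.
- *Aligning diabetes would make the VTE and CV results comparable.* The protocol describes them separately and does not compare them. They already differ elsewhere: on-treatment hypertension needs at least 3 dispensings for VTE (or 2 for large packs) but 1 for CV.

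**Conclusion.** The inconsistency is real and unexplained, and the row followed as written under-detects drug-treated diabetes arising on tofacitinib. The strongest contrast is within the CV set, where baseline and on-treatment status rest on different rules for the same condition. The consequence is limited to the CV discontinuation and continuation outcomes and the index-to-Week-16 part of the JAKi UC maintenance-dose outcome.

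The size cannot be derived from the documents. It is probably small, because seven other factors can bring the same patient into the group and because the reported proportion moves only if the missed patients discontinue at a different rate. The conclusion assumes that some patients have qualifying dispensings without a hospital or LTD code, which Section 9.9.1.2 makes plausible but does not quantify. It also assumes that the JAKi outcome uses the on-treatment rows after index. This is a minor point, worth correcting because it is cheap.

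**What to change.** Change the on-treatment CV diabetes row to match the VTE on-treatment row, the CV baseline row and Annex 11: at least one ICD-10 code, or the repeat-dispensing rule for A10* drugs. Derive one diabetes variable and use it in both risk-factor sets. If code-only was intended, state why.

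With the change, fix three details for the CV and VTE on-treatment rows alike:

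- the date of a dispensing-based event, for example the first qualifying dispensing, so that the discontinuation window has an anchor;
- whether the later, confirming dispensings may fall after tofacitinib has stopped;
- whether patients already diabetic at baseline can count as developing diabetes.

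The cost is one table cell, a sentence or two on dating, and a little extra programming; the dispensing rule is already specified for the VTE set. The drawback is that a dispensing date places onset less exactly than a code date.
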